8.5 Expedited Reporting

The Sponsor/designee [REDACTED] will report all relevant information about Suspected Unexpected Serious Adverse Reactions (SUSARs) that are fatal or life-threatening to the Food and Drug Administration (FDA), applicable Competent Authorities in all Member States (including all Institutional Review Boards [IRBs]/Independent Ethics Committees [IECs]), and to the Central Ethics Committees no later than 7 calendar days (CDs) after knowledge by the Sponsor/designee of such a case. Relevant follow-up information will subsequently be communicated within an additional 8 CDs.

All other SUSARs will be reported to the FDA, applicable Competent Authorities in all Member States (including all IRBs/IECs), and to the Central Ethics Committees within a maximum of 15 CDs of first knowledge by the Sponsor/designee.

The Sponsor/designee will also report any additional expedited safety reports required in accordance with the timelines outlined in country-specific legislation.

The Sponsor/designee will also inform all Investigators as required per local regulation.

The requirements above refer to the requirements relating to study drug.

8.5.1 Project Specific Exemption From SAE Immediate Reporting to Health Authorities, Ethics Committees, and IRBs

The FDA guidance documents titled “Guidance for clinical investigators, sponsors, and IRBs. Adverse event reporting to IRBs – improving human subject protection” and “Guidances for

industry and investigators on safety reporting requirements for investigational new drug applications and bioavailability/bioequivalence studies" state that only AEs which are unexpected, serious, and would have implications for the conduct of the study should be reported in an expedited manner.^{20,21}

Aggregate unblinded analysis by the independent DSMB will be conducted in order to identify safety concerns, such as potential imbalances in event rates between the drug treatment and control groups. Should the DSMB identify any potential safety concerns, they will be able to recommend reporting of these findings to the Health Authorities (HA), Investigators, Ethics Committees, and IRBs. Additionally, the DSMB will have the freedom to determine, based on their ongoing review of the safety data, if any of the exempted AEs should be changed to become subject to expedited reporting from that point on. A safety report will be submitted if an aggregate analysis indicates the anticipated SAEs are occurring more frequently in the treatment group compared to the placebo group.

8.6 Special Situation Reports

Special situation reports include reports of overdose, misuse, abuse, medication error, and reports of adverse reactions associated with product complaints.

- **Overdose:** Refers to the administration of a quantity of a medicinal product given per administration or cumulatively (accidentally or intentionally), which is above the maximum recommended dose according to the protocol. Clinical judgment should always be applied. In cases of a discrepancy in the drug accountability, overdose will be established only when it is clear that the participant has taken additional dose(s), or the Investigator has reason to suspect that the participant has taken additional dose(s).
- **Misuse:** Refers to situations where the medicinal product is intentionally and inappropriately used in a way that is not in accordance with the protocol instructions or local prescribing information and may be accompanied by harmful physical and/or psychological effects.
- **Abuse:** Is defined as persistent or sporadic, intentional excessive use of a medicinal product, which is accompanied by harmful physical or psychological effects.
- **Medication error:** Is any unintentional error in the prescribing, dispensing, or administration of a medicinal product by a healthcare professional, participant, or consumer, respectively. The administration or consumption of the unassigned treatment and administration of an expired product are always reportable as medication errors; cases of participants missing doses of investigational product are not considered reportable as medication errors.
- **Product complaint:** Is defined as any written, electronic, or oral communication that alleges deficiencies related to the identity, quality, durability, reliability, safety, effectiveness, or performance of a drug or device after it is released for distribution. A special situations form will only be completed if a complaint is associated with an adverse drug reaction.

All special situation events as described above must be reported on the special situation report form and faxed/mailed to [REDACTED] (contact information listed below) within 24 hours of knowledge of the event. All AEs associated with these special situation reports should be reported as AEs or SAEs as well as recorded on the AE eCRF and/or the SAE report form. Details of the symptoms and signs, clinical management, and outcome should be provided, when available.

Safety Contact Information: [REDACTED]

8.7 Clinical Laboratory Evaluations

Clinical laboratory evaluations (including a full serum chemistry panel, hematology, coagulation, and urinalysis) will be collected at visits specified in the Schedule of Procedures ([Appendix A](#)). A limited serum chemistry panel will also be collected per the Schedule of Procedures (Appendix A). All safety laboratory samples should be collected while the participant is fasting (a minimum of 8 hours) and prior to the next dose of study drug (at applicable visits). Assessment of laboratory eligibility criteria will be based on central laboratory values obtained within timeframes defined in the inclusion and exclusion criteria.

Urinalysis will be performed locally by dipstick analyses from a sample of mid-stream urine. In case of abnormal results, microscopy and other assessments will be performed at the local laboratory and the abnormality recorded as an AE.

Please see [Appendix B](#) for a complete list of laboratory analytes.

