8.1 Adverse Events

An AE is defined as any untoward medical occurrence in a clinical investigation participant administered a pharmaceutical product, which does not necessarily have a causal relationship with this treatment. An AE can therefore be any unfavorable and/or unintended sign (including an abnormal laboratory finding), symptom, or disease temporally associated with the use of an investigational medicinal product, whether or not related to the investigational medicinal product. All AEs, including observed or volunteered problems, complaints, or symptoms, are to be recorded on the appropriate eCRF.

AEs, which include clinical laboratory test variables, will be monitored and documented from the time of signing of informed consent at Screening until the EOS Visit (approximately 35 days after the EOT Visit). Participants should be instructed to report any AE that they experience to the Investigator, whether or not they think the event is due to study treatment. Beginning at the time of signing of informed consent, Investigators should make an assessment for AEs at each visit and record the event on the appropriate AE eCRF.

Wherever possible, a specific disease or syndrome rather than individual associated signs and symptoms should be identified by the Investigator and recorded on the eCRF. However, if an observed or reported sign or symptom is not considered a component of a specific disease or syndrome by the Investigator, it should be recorded as a separate AE on the AE eCRF. Additionally, the condition that led to a medical or surgical procedure (eg, surgery, endoscopy, tooth extraction, or transfusion) should be recorded as an AE, not the procedure itself.

Any medical condition already present at Screening should be recorded as medical history and not be reported as an AE unless the medical condition or signs or symptoms present at Baseline change in severity, frequency, or seriousness at any time during the study. In this case, it should be reported as an AE.

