Clinically significant abnormal laboratory or other examination (eg, ECG) findings that are detected during the study or are present at Screening and significantly worsen during the study should be reported as AEs, as described below. The Investigator will exercise his/her medical and scientific judgment in deciding whether an abnormal laboratory finding or other abnormal assessment is clinically significant. Clinically significant abnormal laboratory values occurring during the clinical study will be followed until repeat tests return to normal, stabilize, or are no longer clinically significant. Abnormal test results that are determined to be an error should not be reported as an AE.

Laboratory abnormalities or other abnormal clinical findings (eg, ECG abnormalities) should be reported as an AE if any of the following are applicable:

- If an intervention is required as a result of the abnormality;
- If action taken with the study drug is required as a result of the abnormality; or
- Based on the clinical judgment of the Investigator.

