8.7.4 Managing Abnormal and Critical Laboratory Values

Any laboratory test result abnormality that fulfills the criteria for an SAE will be reported as such on the appropriate AE and SAE eCRF. Any treatment-emergent abnormal laboratory result that is clinically significant, ie, meets 1 or more of the following criteria, will be recorded as a single diagnosis on the AE eCRF:

- Is accompanied by clinical symptoms;
- Leads to a change in study drug (eg, study drug interruption or permanent discontinuation); and/or
- Requires a change in concomitant therapy or a medical intervention (eg, the addition of, interruption of, or discontinuation of, or any other change in a concomitant medication, therapy, or treatment).

These criteria apply to any protocol and non-protocol-specified safety and/or efficacy laboratory results from tests performed after the first dose of study drug that meet clinical significance criteria. These criteria do not apply to any abnormal laboratory test results which fall outside the laboratory reference range, but which do not meet clinical significance criteria (these will be analyzed and reported as laboratory abnormalities) or those which are a result of an AE or an endpoint which has already been reported.

The Investigator is responsible for reviewing laboratory test results and determining whether an abnormal value in an individual participant represents a clinically significant change from the participant's Baseline values. In general, laboratory abnormalities without clinical significance should not be recorded as AEs. Where applicable, the clinical sequelae, not the laboratory abnormality, should be recorded as the AE.

Critical laboratory values are values that may warrant medical intervention to avoid possible harm to a participant. Critical laboratory values will be defined in the Laboratory Manual for the study, and the Medical Monitor and Investigator will be notified of the occurrence of a critical laboratory value (critical high or critical low) by a special annotation (flag) in the laboratory reports provided to the sites.

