Leukocyte esterase	Microscopy [1]
Nitrite	pH
Protein	Urobilinogen

1. Urinalysis will be performed locally by dipstick analyses from a sample of mid-stream urine. In case of abnormal results, microscopy and other assessments will be performed at the local laboratory and the abnormality recorded as an adverse event.

Other Laboratory Analytes

Aldosterone	Apolipoprotein A1
High sensitivity C-reactive protein	Lipoprotein (a)
Urine albumin-creatinine ratio	Urine protein-creatinine ratio

APPENDIX C: DIAGNOSTIC SCORING TABLE FOR FAMILIAL HYPERCHOLESTEROLEMIA (CONSTRUCTED BY THE DUTCH LIPID CLINIC NETWORK)

Criteria	Score
Family history	
a) First-degree relative known with premature (men <55 years, women <60 years) coronary and vascular disease; OR	1
b) First-degree relative known with LDL-C >95 th percentile; AND/OR	
a) First-degree relative with tendon xanthomata and/or arcus cornealis; OR	2
b) Children <18 years with LDL-C >95 th percentile.	
Clinical history	
a) Patient has premature (men <55 years, women <60 years) coronary artery disease	2
b) Patient has premature (men <55 years, women <60 years) cerebral or peripheral vascular disease	1
Physical examination	
a) Tendon xanthomata	6
b) Arcus cornealis below the age of 45 years	4
Laboratory analysis ¹	
a) LDL-C >330 mg/dL (>8.5 mmol/L)	8
b) LDL-C 250-329 mg/dL (6.5-8.5 mmol/L)	5
c) LDL-C 190-249 mg/dL (4.9-6.4 mmol/L)	3
d) LDL-C 155-189 mg/dL (4.0-4.9 mmol/L)	1
DNA analysis	
a) Presence of functional LDL-R mutation (in the LDL-R, ApoB, or PCSK9 gene)	8
Diagnosis of familial hypercholesterolemia is:	
Certain when	>8 points
Probable when	6-8 points
Possible when	3-5 points
1. High-density lipoprotein cholesterol and triglycerides are normal.	
ApoB = apolipoprotein B; DNA = deoxyribonucleic acid; LDL-C = low-density lipoprotein cholesterol; LDL-R = low-density lipoprotein receptor; PCSK9 = proprotein convertase subtilisin/kexin type 9.	
Sources:	
World Health Organization. Familial hypercholesterolaemia (FH): report of a second WHO consultation . 04 September 1998. http://whqlibdoc.who.int/hq/1999/WHO_HGN_FH_CONS_99.2.pdf . Accessed 21 April 2022	

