7. A single 12-lead ECG will be performed in the supine position after 10 minutes of rest.
8. Participants must fast for a minimum of 8 hours prior to samples being collected.
9. Samples should be collected prior to study drug administration.
10. Urinalysis will be performed locally by dipstick analyses from a sample of mid-stream urine. In case of abnormal results, microscopy and other assessments will be performed at the local laboratory and the abnormality recorded as an AE.
11. A PK sample will be collected prior to study drug administration for trough measurement of obicetrapib in plasma. At Visits 2, 5, and 7, participants should take study drug after a trough PK sample has been drawn.
12. The PK sample at Visit 4 is not designated in the protocol, however the PK will be assessed using residual serum from the Day 84 limited chemistry panel to confirm patients are taking IP.

AE = adverse event; ApoA1 = apolipoprotein A1; BMI = body mass index; CV = cardiovascular; ECG = electrocardiogram; EOS = End of Study; EOT = End of Treatment; ET = Early Termination; FSH = follicle-stimulating hormone; hsCRP = high sensitivity C-reactive protein; Lp(a) = lipoprotein (a); PK = pharmacokinetic(s); TSH = thyroid-stimulating hormone; UACR = urine albumin-creatinine ratio; UPCR = urine protein-creatinine ratio; V = Visit.

2.2.2 *Sample Size Determination*

Enrollment of approximately 300 participants globally is planned for this study.

Assuming an approximate 5% drop out rate, approximately 285 participants will be evaluable for efficacy. This sample size of at least 285 evaluable participants will provide more than 90% power to detect a 30% reduction of LDL-C (standard deviation 15%) levels in the obicetrapib group compared to the placebo group at a 1-sided significance level of 0.025. This sample size will also contribute to sufficient participant exposure and safety data.

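### The protocol's unconditional rule that an abnormal urine dipstick is an AE conflicts with its own AE rules in Sections 8.1 and 8.7.4, so recording can differ by site

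*Protocol*

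**What the plan says.** **The dipstick rule.** Protocol Section 8.7 has urinalysis done locally by dipstick and continues: "In case of abnormal results, microscopy and other assessments will be performed at the local laboratory and the abnormality recorded as an AE". Appendix A footnote 10 repeats this. Appendix B has "microscopy and other assessments will be performed at the local laboratory and the abnormality recorded as an adverse event", and SAP Table 1 footnote 10 has "microscopy and other assessments will be performed at the local laboratory and the abnormality recorded as an AE". None of the four adds a qualifier.

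**The general AE rules.**
- Section 8.7.4: "In general, laboratory abnormalities without clinical significance should not be recorded as AEs". Results outside the reference range that miss its significance criteria are handled as laboratory abnormalities.
- Section 8.1 relies on the Investigator's judgement in "deciding whether an abnormal laboratory finding or other abnormal assessment is clinically significant".
- Section 8.1 on pre-existing conditions: "Any medical condition already present at Screening should be recorded as medical history and not be reported as an AE unless" they change in severity, frequency or seriousness. Clinically significant abnormal findings that "are present at Screening and significantly worsen during the study should be reported as AEs".
- Section 8.1 also keeps results found to be erroneous out of the AE data.

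**Use of the data.** SAP 3.5.1 tabulates treatment-emergent AEs, including non-serious preferred terms seen in more than 2% of either group. Safety is summarised without inference (Protocol 9.2.2, SAP 3.5).

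**The concern.** A site that follows Section 8.7 literally enters an isolated trace of protein, ketones or leukocyte esterase as an AE, whatever the Investigator thinks of it and whether or not it was there before. A site that follows Section 8.7.4 enters nothing. About 60 sites read dipsticks locally, and no passage tells them which rule prevails. Part of the AE count would then reflect which section a site applied and not what happened to participants. The exposed outputs are the any-TEAE row and the preferred terms for urinary findings.

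**Working it through.** The documents state no AE or dipstick count, so there is no figure to reproduce. The check compares the rules and then bounds the size on assumed rates.

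**1. The rules side by side.**

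| Question | Dipstick rule | Sections 8.1 and 8.7.4 |
|---|---|---|
| Abnormal but not clinically significant | AE | In general not an AE; laboratory data |
| Who decides | Nobody; automatic | The Investigator |
| Present at Screening, unchanged | AE on the literal wording | Not an AE |
| Result turns out to be an error | AE on the literal wording; not conditional on microscopy | Not an AE |
| What is entered | The abnormality | A single diagnosis or, where applicable, the clinical sequelae |

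**2. Is there an exception clause?** None was found. Section 8.7.4 says its criteria cover any protocol-specified safety laboratory result obtained after first dose. The end-of-treatment dipstick therefore falls under both rules. Dipsticks before dosing meet Section 8.1, because AE collection starts at consent.

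**3. Which dipsticks can reach the TEAE tables?** The schedule shows three: Screening, Day 1 and one late visit. The column of the late mark is unclear in the text available. It is read here as V7/EOT/ET for two reasons: the ECG row has the same pattern and SAP 3.5.5 places that ECG at Visit 7/EOT/ET, and the list of EOS assessments in Protocol 3.1 omits urinalysis. Two of the three thus fall before or at first dose. Under a usual TEAE definition, only the V7 dipstick feeds the tables.

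**4. Size.** Inputs: N of about 300 (Protocol 9.2.5), taken as the approximate Safety Population. The 285 in that section is the number evaluable for efficacy and is not the denominator here. The abnormality rate p per dipstick is assumed.

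Participants with a V7 dipstick AE = N × p. Records over all three dipsticks = 3 × N × p.

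| p (assumed) | V7: 300 × p | All three: 900 × p | Of which before or at first dose: 600 × p |
|---|---|---|---|
| 2% | 6 | 18 | 12 |
| 5% | 15 | 45 | 30 |
| 10% | 30 | 90 | 60 |
| 20% | 60 | 180 | 120 |
| 30% | 90 | 270 | 180 |

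These are upper bounds. They assume that every site follows Section 8.7, that everyone attends V7 and that every abnormal result is a new record. They also include clinically significant findings, which would be AEs under either rule.

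**5. The 2% table.** With 2:1 allocation the groups are about 200 and 100. More than 2% means at least 5 of 200 (2% is 4) or at least 3 of 100 (2% is 2). The cut-off applies to each preferred term, whereas p above is for any abnormality. Appendix B lists nine dipstick analytes. If p spread evenly over nine terms with one per participant, p = 5% would give 5/9 = 0.56% per term, below the cut-off. Terms would pass it only above 9 × 2% = 18%. A concentrated pattern would pass it sooner. The documents do not settle which applies.

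**6. Effect between groups.** If a share p in both groups gains a dipstick AE independently of other AEs, an any-TEAE rate r becomes r + (1 − r)p, and a gap between groups is multiplied by (1 − p). With assumed rates of 50% and 60%:
- p = 5% gives 52.5% and 62%, a gap of 9.5 points instead of 10.
- p = 30% gives 65% and 72%, a gap of 7 points.

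Other preferred terms do not move.

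**The case against.** The best defence is that the dipstick rule is deliberate. It is worded consistently in four places. Section 8.1 counts an abnormal laboratory finding as a possible AE, and its list of triggers says when to report without saying that nothing else may be reported. Section 8.7.4 speaks only of what holds in general. Section 8.7 could therefore be a specific, over-inclusive rule that sits beside the general ones. This reading is possible, and it would be too strong to say that the sections flatly forbid what Section 8.7 orders. But no passage states an exception, and Section 8.7.4 claims all protocol-specified safety results after first dose. A site cannot tell which rule applies, so a clarification is needed on either reading.

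The defence also limits the consequences, and these limits stand:
- A reader might infer that AE tables will fill with non-events. There is no abnormality rate in the documents to support that.
- A reader might infer that a pre-existing finding is counted again at end of treatment. No passage orders a second record, and an unchanged finding already recorded before dosing is not treatment-emergent in the usual sense.
- A reader might infer that renal safety monitoring is blurred. The renal events of special interest are defined by eGFR and serum creatinine, with shift tables for the two urine ratios; none uses the dipstick.
- A reader might infer a bias between arms. Treatment is blinded and the rule is the same in both groups, so neither arm is favoured.

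**Conclusion.** The conflict is real and rests on the text alone. Four passages make every abnormal dipstick an AE without condition, while Sections 8.1 and 8.7.4 apply tests of significance, change and error, and nothing says which prevails. The result is site-dependent recording that can inflate the any-TEAE row and urinary-finding terms by an unknown amount.

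The range of 6 to 90 participants depends on the assumed 2% to 30% and is an upper bound. Confining the effect mainly to V7 assumes the schedule reading above and a usual TEAE definition, which the SAP text does not spell out. The harm is non-differential noise in descriptive tables. Efficacy and the renal events of special interest are unaffected. Trivial dipstick findings should also not reach the tables of serious, fatal or discontinuation-related events. The point deserves correction because it is a conflicting instruction with a cheap remedy, not because it threatens the trial's conclusions.

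**What to change.** In Section 8.7, Appendix A footnote 10, Appendix B and SAP Table 1 footnote 10, make the recording conditional, for example: recorded as an AE if it meets the criteria of Sections 8.1 and 8.7.4. If the sponsor does intend an exception for dipsticks, Sections 8.1 and 8.7.4 should say so. Report the remaining dipstick abnormalities as laboratory data in the Baseline to end-of-treatment shift tables that SAP 3.5.3 already plans for all parameters. A written TEAE definition in the SAP would secure the exclusion of findings from before dosing.

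First confirm that local dipstick results, including those not reported as AEs, are captured in the eCRF. No passage says so, and SAP 3.5.3 plans listings for chemistry and hematology only. If the AE form is the only route of capture, the change would lose data or need a new field.

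Otherwise the cost is one sentence in four places and a note to sites. The small downside is that trivial dipstick findings would appear only in the laboratory tables.
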